Experience has shown that in nearly all clinical trials with sorafenib (Nexavar[®]) there are patients who are continuing to receive sorafenib after the study has met its primary endpoint. The options to provide sorafenib to these patients who have a non-approved/reimbursed tumor type are through a clinical trial, through a Post-Trial Access Program or through any other mechanism (e.g. local access program) in accordance with local legal and compliance rules.^m The intention of this clinical study 12311 (STEP program) is to enable patients who are still benefiting from *treatment* in a completed clinical trial to continue to receive *treatment*.ⁿ

Please refer to the sorafenib Investigator Brochure and any additional data supplied by the Sponsor.

2. Study objectives - amended

The primary purpose of the STEP program is to enable patients, currently receiving sorafenib (Nexavar) in a Bayer/Onyx sponsored clinical trial, to continue sorafenib treatment after their respective study has met its primary endpoint and/or has reached the end as defined in the original protocol. Patients will be able to continue treatment until **(i)** the treating physician feels the patient is no longer benefiting from the treatment or **(ii) *the treatment*ⁿ** becomes commercially available and reimbursed for the respective indication as applicable in the country in which the patient lives ***and the patient can obtain suitable amounts of drug for treatment through standard mechanisms of commercial availability (ie, there should be no interruption in the patient's treatment schedule when switching to commercially available product)*^o** or **(iii)** the patient can join a Post-Trial-Access Program, another study or can receive sorafenib through

m: Added Post-Trial Access Program with Amendment 8. See Section 10.6.3, Modification 3.

n: Reference to subjects receiving single-agent sorafenib was modified under Amendment 3 to allow inclusion of subjects receiving sorafenib in combination with other drugs, specifically, subjects from the SEARCH trial receiving sorafenib and erlotinib and subjects from the RESILIENCE trial receiving sorafenib and capecitabine. See Section 10.3, Modification 5.

o: Under Amendment 3, it was clarified that there should be no interruption in a patient's treatment schedule when switching to commercially available product. See Section 10.3, Modification 6.

any other mechanism (e.g. local access program) in accordance with local legal and compliance rules, with no cost to the patient with respect to sorafenib.^p

An additional objective is the assessment of the safety of Nexavar or Nexavar combination treatment.^{q r}

3. Investigator(s) and other study participants

Information regarding additional key personnel involved in the conduct of the study, including names and contact details of participating Investigators, monitors, clinical laboratories, technical departments and/or institutions, as well as information on members of additional study committees, will be found in the study files of the Sponsor and on site if requested.

4. Investigational plan

4.1 Study Design and Plan - amended

This is an open label clinical trial that will enable patients receiving sorafenib (Nexavar) in a completed Bayer/Onyx sponsored clinical trial to continue treatment. A completed study is one that has passed the official statistical and regulatory endpoints and/or has reached its end, as outlined in that protocol.

The patients ***in this open-label clinical trial*** will continue receiving single-agent sorafenib (Nexavar)^s or sorafenib and capecitabine ***combination*** if transferred from Study 12444 (RESILIENCE)^t at the same dose and schedule as in their original Clinical Trial.

p: Added clarification for continuation on study drug with Amendment 8. See Section 10.6.5, Modification 5.

q: These additional objectives were added in Amendment 3. See Section 10.3 Modification 1 and Modification 2.

r: Objective modified by Amendment 7 to remove overall survival (OS). See Section 10.5.2, Modification 2.

s: Reference to erlotinib removed since none of the subjects that transferred into this study were assigned to erlotinib from study 12917. See Section 10.4, Amendment 4, Modification 2.

t: Reference to subjects receiving single agent sorafenib was modified under Amendment 3 to allow inclusion of subjects receiving sorafenib in combination with other drugs, specifically, subjects from the SEARCH trial receiving sorafenib and erlotinib and subjects from the RESILIENCE trial receiving sorafenib and capecitabine. See Section 10.3, Amendment 3, Modification 5.

Patients will continue receiving sorafenib (Nexavar; ***as single agent or combination treatment***),^t as long as the treating physician feels the patient is continuing to benefit from treatment or until sorafenib (***as single agent or combination treatment***) becomes commercially available and reimbursed for the respective indication in the country in which the patient lives or until being switched to any other form of drug supply with no interruption in the patient's treatment schedule.^u The patient may also continue ***treatment***^v until he/she withdraws consent, is non-compliant, is lost to follow up, or if an unacceptable toxicity occurs.

Prior to being dispensed study medication for this long term extension clinical trial, patients will be required to complete their End of Treatment visit in their originating study. Once the End of Treatment visit in the originating study is complete, patients will be required to provide informed consent for this long term extension clinical trial. Patients will continue with single agent sorafenib (Nexavar)^w ***or sorafenib and capecitabine if transferred from Study 12444 (RESILIENCE)***^{x y} at the same dose and schedule the patient was receiving in their original clinical trial.

Sorafenib (Nexavar) will be provided as 200 mg tablets. ^z ***Capecitabine is available in many countries including generic sources and will be commercially supplied 150 mg and 500mg tablets^{aa} for patients receiving the sorafenib/capecitabine combination and transferring from***

u: Added clarification for continuation on study drug with Amendment 8. See Section 10.6.5, Modification 5.

v: Reference to subjects receiving single agent sorafenib was modified under Amendment 3 to allow inclusion of subjects receiving sorafenib in combination with other drugs, specifically, subjects from the SEARCH trial receiving sorafenib and erlotinib and subjects from the RESILIENCE trial receiving sorafenib and capecitabine. See Section 10.3, Modification 5.

w Reference to erlotinib removed since none of the subjects that transferred into this study were assigned to erlotinib from study 12917. See Section 10.4, Modification 2.

x: Reference to subjects receiving single agent sorafenib was modified under Amendment 3 to allow inclusion of subjects receiving sorafenib in combination with other drugs, specifically, subjects from the SEARCH trial receiving sorafenib and erlotinib and subjects from the RESILIENCE trial receiving sorafenib and capecitabine. See Section 10.3, Modification 5.

y Reference to capecitabine was removed with Amendment 8. See Section 10.6.4, Modification 4.

z Sentence removed since none of the subjects that transferred into this study were assigned to erlotinib. See Section 10.4, Amendment 4, Modification 2.

aa Text changed to clarify that capecitabine will be supplied commercially and not by the sponsor under Amendment 4. See Section 10.4, Modification 3.

Study 12444 (RESILIENCE).^{bb} The patient should be evaluated according to Good Medical Practices as well as local therapeutic and diagnostic standards. The patients should be evaluated by a study physician for safety at least once every 8 weeks and more frequently as needed. The protocol allows for a ± 7 days window when scheduling any visit. Physicians can choose to continue to see the patients every 8 weeks in a face to face visit. At least every other visit must be a mandatory on site visit for examination and drug dispensing, with the other visit being either in person or as a phone call. It is at the discretion of the investigator based on the patient's current condition and adverse event profile to determine if the next visit will be performed on site or as a phone visit. Any scheduled phone visit is mandatory and it will be at the discretion of the investigator to decide if that phone visit is sufficient. If the patient needs a physical examination, the visit will be performed on site. If the investigator feels the patient is stable with no new safety concerns nor new AEs in between visits, a phone call with labs, ECOG and review of AEs would be enough^{cc}. Once every 8 weeks^{cc} safety evaluations include vital signs (ie, heart rate, blood pressure, temperature) only when the visit is on site, **Eastern Cooperative Oncology Group (ECOG) performance status**, laboratory evaluations may be performed by local accredited lab which need to have PI signoff within a week of drawing^{dd} (hematology, ALT, AST, lipase and amylase, PT-INR as applicable for anticoagulated patients) and a review of any new or ongoing adverse event or concomitant medications as well as study medication taken during the visit interval. All adverse events, laboratory data, **ECOG performance status and survival status (dead or alive and date of death or date of last contact)**,^{ee} as well as End of Treatment information and study medication taken must be clearly and accurately recorded in the Case Report Form provided. All other data, including but not limited to, vital signs, concomitant

bb: Information on the erlotinib and capecitabine formulations was added under Amendment 3. See Section 10.3, Modification 5. Reference to capecitabine was removed with Amendment 8. See Section 10.6.4, Modification 4.

cc Safety follow-up adjusted by Amendment 7 to lessen the travel burden on patients. See Section 10.5.3, Modification 3.

dd Laboratory evaluations have been adjusted by Amendment 7 to ensure these are not missed. See Section 10.5.4, Modification 4.

ee: Survival and ECOG performance status were added to the Case Report Form as of Amendment 3. See Section 10.3 Modification 1 and Modification 2.

medications must be recorded in the patient's source documents and may be requested at the discretion of the Sponsor.

Following the End of Treatment assessments from the original study, the following information will be recorded in the long term extension CRF: demography, date of first dose of sorafenib (Nexavar) in originating study^{ff} date of first dose of capecitabine if the patient is transferred from RESILIENCE (Study 12444),^{gg} originating study number, *ECOG performance status and survival status (dead or alive and date of death or date of last contact)*^{hh} and ongoing adverse events.

In the event the patient experiences a treatment related Serious Adverse Event, based on the definition outlined in Section 7 of this document, this event must be reported to Bayer Global Drug Safety immediately (within 24 hours of awareness) using the forms provided, and recorded in the CRF.

In the event that another mechanism of continued drug supply is established, the present study will end when all patients have transitioned to any new drug supply program or discontinued from this study for another reason (e.g. consent withdrawal, lost to follow-up, death, sponsor decision). Until the transition, patients will continue to follow all the procedures and visits required in the current version of the protocol.ⁱⁱ

4.2 Selection of Study Population

Patients who remain ongoing in a Bayer/Onyx sponsored Clinical Trial that has reached its statistical, regulatory and/or study end and who, in the opinion of the Investigator, still benefiting from treatment, will be eligible for entry into this study (STEP program).

^{ff} Sentence removed since none of the subjects that transferred into this study were assigned to erlotinib. See Section 10.4, Modification 2.

^{gg} Participation of subjects from the SEARCH trial (Study 12917) or from the RESILIENCE trial (Study 2444) was added under Amendment 3 See Section 10.3, Modification 5.

^{hh} These additional objectives were added in Amendment 3. See Section 10.3, Modification 1 and Modification 2.

ⁱⁱ Added clarification for ending the study with Amendment 8. See Section 10.6.6, Modification 5.

4.2.1 Inclusion Criteria

- Patients, who are participating in a previous Bayer/Onyx sponsored study that has reached its endpoint (statistical and regulatory or study end), and who are, in the opinion of the Investigator, expected to continue to have an overall positive benefit/risk from continuing treatment.
- Patients who have signed informed consent for this long term extension program.
- Women of childbearing potential and men must agree to use adequate contraception prior to study entry and for the duration of study participation, including the 30 days period after last study drug dosing. The investigator should advise the patient how to achieve an adequate contraception.
- Women of childbearing potential who have a negative pregnancy test within 7 days of the first dose of sorafenib in this long term extension program.
- Patient is receiving sorafenib (Nexavar) as a monotherapy in their originating protocol. Patients who were being treated with sorafenib (Nexavar) in combination with other chemotherapies in the original study, but continued on single agent sorafenib (Nexavar) after discontinuation of the combination agent will be eligible.
- Patients who are receiving concurrent combination with sorafenib (Nexavar) and TACE (transarterial chemoembolization) in their originating study will be eligible.^{jj} ^{kk}
- ***Patients who are receiving concurrent combination with sorafenib (Nexavar) and capecitabine in their originating Study 12444 (RESILIENCE) will be eligible.***
- Patients who have completed the End of Treatment assessments in their originating study. Every effort should be made to conduct the End of Treatment visit such that the patient does not have any interruption of sorafenib dosing.

jj: The inclusion criterion regarding eligibility of subjects receiving combination sorafenib and TACE in their originating studies was added under Amendment 2. See Section 10.2.

kk Reference to erlotinib removed since none of the subjects that transferred into this study were assigned to erlotinib from study 12917. See Section 10.4, Modification 2.

4.2.2 Exclusion Criteria

- Any condition that is unstable or that could jeopardize the safety of the patient (please refer to the Investigator Brochure and product labeling safety sections).
- History of cardiac disease: congestive heart failure>NYHA Class 2 (Appendix 11.2) or uncontrolled hypertension
- Myocardial infarction (MI) within the last 3 months
- Symptomatic metastatic brain or meningeal tumors
- Previous or concurrent cancer that is distinct in primary site or histology from the cancer being evaluated in this study EXCEPT cervical carcinoma in situ, treated basal cell carcinoma, superficial bladder tumors (Ta, Tis & T1) or any cancer curatively treated > 5 years prior to study entry.
- Patients with seizure disorder requiring medication (such as steroid anti-epileptics)
- Substance abuse, medical, psychological or social conditions that may interfere with the patient's participation in the study or evaluation of the study results
- Any condition which could jeopardise the safety of the patient and his/her compliance in the study

Excluded therapies and medications, previous and concomitant:

- Concurrent anti-cancer chemotherapy, except TACE (transarterial chemoembolization)^{ll mm nn} and capecitabine

ll: The exclusion criterion regarding concurrent anti-cancer chemotherapy was modified under Amendment 2. See Section 10.2.

- Concurrent immunotherapy (including monoclonal antibodies), during or within 30 days prior to start of study drug^{oo}
- Concurrent hormonal therapy, except for bisphosphonates, during or within 30 days prior to start of study drug^{oo}
- Concomitant Rifampicin and St John's Wort (Warfarin may be used only with very close monitoring.)
- Radiotherapy during study or within 3 weeks of start of study drug. [Palliative radiotherapy will be allowed as described in the Prior and Concomitant Therapy Section 4.5.8.]
- Concomitant use of potent inhibitors of CYP 3A4 including ketoconazole, itraconazole and ritonavir. Consumption of grapefruit juice should also be avoided.

4.3 Removal of Subjects from Study

Subjects may be withdrawn from the study for the following reasons:

- At their own request or at the request of their legally acceptable representative.
- If, in the Investigator's opinion, continuation in the study would be detrimental to the subject's well-being.
- At the specific request of the Sponsor.
- The patient dies.

mm Reference to erlotinib removed since none of the subjects that transferred into this study were assigned to erlotinib from study 12917. See Section 10.4, Modification 2.

nn: Participation of subjects from the SEARCH trial (Study 12917) or from the RESILIENCE trial (Study 12444) was added under Amendment 3. In Amendment 4, reference to erlotinib is removed, as no subjects was enrolled into this study from study 12917 taking the combination of erlotinib and sorafenib. Therefore, capecitabine is not an excluded therapy. See Section 10.3, Modification 5.

oo: The exclusion criterion regarding concurrent anti-cancer chemotherapy was modified under Amendment 2. See Section 10.2.

Also subjects must discontinue treatment for the following reasons:

- Substantial non-compliance.
- Patients with clinical signs or laboratory tests results consistent with pregnancy. Pregnancy will be reported by the Investigator on a Pregnancy Monitoring Form (PMF) following the same timelines as a Serious Adverse Event.
- The patient uses illicit drugs or other substances that may, in the opinion of the Investigator, have a reasonable chance of contributing to toxicity or otherwise interfering with results.
- Occurrence of unacceptable toxicity.
- When Nexavar is commercially available and reimbursed for the respective indication in the country in which the patient lives.
- The patient is lost to follow-up.

In all cases, the reasons for withdrawal must be recorded in the case report form and patient's medical record. All patients who discontinue due to adverse events or clinical laboratory abnormalities should be followed up until they recover or stabilize, and the subsequent outcome recorded.

If any patient should die during the trial or within 30 days of the patient's last dose of sorafenib (Nexavar), the Investigator should inform Bayer by completing the SAE Complimentary Form and Adverse Event page for the study.

The cause and date of death should also be recorded on the End of Treatment page, as applicable.

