4.6 Study Variables

The primary objective is to enable patients receiving sorafenib (Nexavar) in a completed Bayer/Onyx-sponsored Clinical Trial to continue treatment in this extension program.

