In accordance with local regulatory requirements, specific mention of the head of the center for sites in Japan has been added to [Section 4.4](#), Premature Termination of Study/Closure of Centre and [Section 5.1](#), Ethics Committee (EC) or Institutional Review Board (IRB).

Modification 4: Adverse Events

In accordance with local regulatory requirements in Japan, specific language has been added to [Section 7.2](#), Adverse Event Monitoring and Section [Section 7.3.3](#), Unexpected Adverse Event

In accordance with local Japanese regulatory requirements, [Section 7.3.2](#), Serious Adverse Event, was modified to clarify that, in Japan, any adverse event leading to hospitalization or

prolongation of hospitalization is to be considered as serious regardless of the length of hospitalization or prolongation of hospitalization.

Modification 5: Inclusion of Subjects From the SEARCH Study (Study 12917) and the RESILIENCE Study (Study 12444)

The Sponsor has made the decision to allow patients from the SEARCH study, in which patients receive sorafenib in combination with erlotinib, or the RESILIENCE Study, in which patients receive sorafenib in combination with capecitabine, to receive continued treatment in the Sorafenib Long Term Extension Program (STEP). Therefore, all necessary information regarding the inclusion of these subjects into STEP has been included in the protocol under this amendment (Amendment 3).

The protocol sections affected by the inclusion of these subjects are [Section 1](#), Introduction, [Section 2](#), Study Objectives, [Section 4.1](#), Study Design and Plan, [Section 4.2.1](#), Inclusion Criteria, [Section 4.2.2](#), Exclusion Criteria, [Section 4.5.1](#), Treatments to be Administered, [Section 4.5.2](#), Dose Modification, [Section 4.5.3](#), Identity of Investigational Product(s), [Section 4.5.5](#), Selection of Doses in the Study, [Section 4.5.8](#), Prior and Concomitant Therapy, and [Section 11](#), Study Flow Chart.

Modification 6: Minor Changes

Contact names for the Study Manager, Statistician, and Medical Expert were updated on the title page of the protocol.

The information in [Section 2](#) regarding the conditions whereby patients may receive treatment under this protocol was modified slightly to clarify that, if switching to commercially available product, there should be no interruption in the patient's treatment schedule.

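### Protocol Section 4.3 makes national availability and reimbursement a mandatory stop for study drug, without the Section 2(ii) condition that the patient can actually obtain commercial supply without a gap

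*Protocol*

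**What the plan says.** Three places in the current body of the protocol describe how a patient leaves the study because sorafenib has become commercially available.

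- **Section 2, route (ii).** The patient may continue until the treatment is available and reimbursed in the country and, joined by 'and', the "patient can obtain suitable amounts of drug for treatment through standard mechanisms of commercial availability". A bracketed explanation adds that the switch should not interrupt the treatment schedule. The footnote to this text reads: "Under Amendment 3, it was clarified that there should be no interruption". SAP Section 2 repeats the whole of route (ii).
- **Section 4.1.** Treatment continues until sorafenib "becomes commercially available and reimbursed for the respective indication in the country in which the patient lives or until being switched" to another form of supply. A no-interruption phrase follows that last alternative.
- **Section 4.3.** The second of its two lists opens "Also subjects must discontinue treatment for the following reasons" and includes: "When Nexavar is commercially available and reimbursed for the respective indication in the country in which the patient lives". The bullet ends there and does not refer to Section 2.

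**The concern.** Section 4.3 is where a site looks to decide when study drug has to stop, and it separates reasons for which a subject may be withdrawn from reasons for which treatment must end. The commercial-availability bullet is in the mandatory list but tests only the situation in the country. The test of the patient's own access appears under the study objectives.

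What is at stake is the purpose of the study. Section 4.6 states: "The primary objective is to enable patients receiving sorafenib (Nexavar) in a completed Bayer/Onyx-sponsored Clinical Trial to continue treatment in this extension program". The protocol guards against a dosing gap at entry, where Section 4.2.1 asks that the end-of-treatment visit be arranged "such that the patient does not have any interruption of sorafenib dosing", and again at commercial exit in Section 2(ii). Followed to the letter, Section 4.3 can take a patient off study drug after national reimbursement starts but before that patient can obtain the commercial product.

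**Working it through.** The protocol states no figure on this point and gives no sample size (Section 6.2), so the check is a comparison of current texts.

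**Step 1. What each statement requires before the commercial exit applies.**

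| Current text | Available and reimbursed in country | Patient can obtain enough drug | No interruption on the commercial switch | Force |
|---|---|---|---|---|
| Protocol 2(ii) | yes | yes | yes | permits continuation until met |
| Protocol 4.1 | yes | no | not in the commercial clause; a phrase follows the separate supply-switch alternative | describes how long treatment continues |
| Protocol 4.3 | yes | no | no | mandatory stop |

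The full condition is present in 1 of 3 protocol statements. The 2 without it include the only one worded as mandatory. SAP Section 2 agrees with protocol Section 2(ii).

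**Step 2. Does the difference produce opposite instructions?** Take a patient in a country where sorafenib is available and reimbursed for the indication, but who cannot yet obtain sufficient commercial drug. Section 2(ii) is not met, so the patient may continue. The Section 4.3 bullet is met, so the patient must stop. The two cannot both be followed.

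**Step 3. Does anything else resolve it?** Section 4.3 has no cross-reference, and no rule states that Section 2 prevails. In Section 4.1 the no-interruption phrase is attached to the switch to another form of supply, text that its footnote attributes to Amendment 8. Even if it is read to cover a commercial switch, the requirement for suitable amounts is missing.

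**Step 4. Intent.** The amendment history is used here only as evidence of intent. Section 10.3.1 says the Section 2 text was "modified slightly to clarify that, if switching to commercially available product, there should be no interruption". The section-by-section changes in 10.3.2 go from 4.2.2 to 4.4 without touching 4.3. Amendment 8 revised exit conditions in Sections 2 and 4.1 only (Section 10.6.5). This fits a safeguard that was never carried through to Section 4.3.

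**Step 5. Size for one patient.** Let L be the number of days by which the patient's commercial access lags national reimbursement.

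- Literal Section 4.3: days without drug can be up to L.
- Section 2(ii): days without drug = 0.
- Difference: up to L − 0 = L days.

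The documents do not give L, the number leaving by this route, or the number still on drug. The 206 in SAP Table 1–1 is the total from all feeder trials, not the number at risk, so the per-patient figure cannot be scaled up.

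**Step 6. Effect on the analysis.** Treatment duration (SAP 6.4) is calculated from actual first and last dose dates, and the treatment-emergent window (SAP 4.5) ends 30 days after the actual last dose. Neither is biased by which exit rule a site applied.

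**The case against.** The best case against is that this is a missing cross-reference. The lists in Section 4.3 are loose catalogues: death appears among reasons a subject may be withdrawn, and loss to follow-up among reasons treatment must stop, and neither works as an instruction. Section 2, its footnote and the SAP make the intended rule plain, so a sensible site would read Section 4.3 as a short form of it. Sections 4.1 and 4.9 also say that, if another supply mechanism is set up, patients keep following study procedures until they have transitioned. Patients are dispensed enough drug to reach the next scheduled visit, and Section 4.3 does not demand a same-day stop. Nothing shows that a gap has occurred, and L days only restates the unknown.

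Part of this stands. The intent is clear, a site reading the two sections together would act correctly, Section 4.1 can arguably be read as carrying the no-interruption half of the condition, and neither the frequency nor the length of any gap is known.

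The rest does not remove the conflict. The transition wording in Sections 4.1 and 4.9 concerns the end of the study under another supply mechanism and does not name commercial supply. Drug in hand does not help a patient whose treatment must be discontinued. Loose drafting elsewhere in Section 4.3 does not make this bullet optional. That Section 2(ii) should govern follows from its history and the study's purpose, but no current text says so.

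**Conclusion.** The concern holds. Two current sections give opposite instructions for a patient whose commercial access lags national reimbursement, and the one worded as mandatory works against the primary purpose. The condition is complete in 1 of 3 protocol statements of this exit. The possible harm is up to L days off drug per affected patient, with L and the number affected unknown. The difference in wording is certain. The consequence depends on a site applying Section 4.3 literally and is smaller where sites already read it in the light of Section 2. The matter is operational and concerns patient care. It should be corrected, but it does not threaten any reported result.

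**What to change.** Extend the Section 4.3 bullet so that the mandatory stop applies only when, in addition to national availability and reimbursement, the "patient can obtain suitable amounts of drug for treatment through standard mechanisms of commercial availability" and the switch causes no break in the treatment schedule, and add a reference to Section 2(ii). Make the same addition to the commercial-availability clause of Section 4.1. This reuses a condition the sponsor has already adopted.

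The drafting cost is one clause in each of two sections, with no new data, procedures or analyses and no SAP change. A protocol amendment may need ethics committee approval (Section 5.1) and needs agreement between sponsor and investigator (Section 5.2). An administrative letter could clarify the point in the meantime; Section 10.4.1 records that route for the earlier mismatch on TACE between Sections 4.2.2 and 4.5.8, later corrected by amendment. The one downside is that a few patients may stay on sponsor supply slightly longer, which Section 2(ii) already allows.
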